Photo-novella, or the use of photographs to tell a story, has been used as a group intervention (photovoice) and as an individual narrative intervention. Photographs as a voice or narrative have been found in a recent systematic review to be effective in participant empowerment, community change, knowledge acquisition, and reaching policymakers.

Digital Stories visually represent first-person narratives that utilize present-day digital culture. Digital stories ask participants to tell a story by creating a short (3-minute) autobiographical vignette synthesizing written text, still and moving imagery, voice, and sound. Digital stories include multiple sensory contexts (e.g., text, spatial, visual, verbal,

and gestures) to convey meaning and can be interpreted on different levels by storytellers and listeners. In a review of digital stories for health promotion, digital stories were found to improve confidence, motivation, behavior change, and/or social change.

At the end of the pilot study, we will provide a voluntary space as a gallery for the critical narratives to be displayed and open to the public. The gallery will be optional for participants who wish to display their critical narratives.

OBJECTIVES:

Our primary objective is to identify the potential use of critical narratives as an elicitation strategy to increase empowerment (e.g., increase in self-esteem), and improve mental health symptoms (e.g., decrease in depression and anxiety, and increase in psychological well-being) in vulnerable populations of SGM individuals of color living with depression. Our secondary objective is to assess the feasibility, acceptability, and appropriateness of critical narratives (photo-novella and digital storytelling) for SGM EA of color. Our specific aims are:

1. Examine the experiences of discrimination and acceptance of SGM EA of color living with depression in their community,
2. Evaluate the impact of CN on empowerment (e.g., self-esteem) and mental health outcomes (depression, anxiety, and psychological well-being) of SGM individuals of color.
3. Understand the acceptability, appropriateness, and feasibility of critical narrative development as a strategy for SGM EA of color.

Outcomes

The study has two primary outcomes addressed in Aim 1 and Aim 2.

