To identify the potential use of critical narratives to elicit empowerment, we will first examine the current experiences of SGM EA of color. Therefore, aim 1 will examine the experiences of stigma (e.g., discrimination) and acceptance of SGM EA of color living with depression and how this may impact mental health treatment seeking in the community. We will conduct in-depth interviews with participants at baseline using an in-depth interview protocol which will include open-ended questions to examine the unique experiences of SGM EA living with multiple marginalized identities (sexual and gender minority, person of color, and living with a mental illness). Utilizing a semi-structured interview protocol, participants will be asked questions about how they identify (i.e., racially/ethnically, sexual identity, and gender identity), their experiences as an LGBTQ+ person in their culture, and their experiences as SGM EA of color in the United States.

Aim 2 will evaluate the impact of CN assignment (photo-novella or digital storytelling) in its ability to address the primary outcomes of:

- 1) Mental health measures:
 - a. decrease depression symptoms utilizing the Patient Health Questionnaire (PHQ-9),
 - b. reduce anxiety symptoms utilizing the Generalized Anxiety Disorder-7 (GAD-7),
 - c. increase psychological well-being using the Flourishing Scale,
- 2) Empowerment measures:
 - a. increase self-esteem using the Rosenberg Self-Esteem Scale,
 - b. increase empowerment utilizing the Rogers empowerment scale,

We will also note the effect of CN assignment to address secondary outcomes of:

- 3) Stigma as a known barrier to mental health treatment seeking:
 - a. decrease internalized mental health stigma using internalized stigma of mental illness (ISMI-9) scale.
 - b. decrease in intersectional minority stress using the LGBTQ+ POC Microaggressions Scale-Brief (LGBTQ+ PCMS-B).
- 4) Intentions to seek care and social support:
 - a. increase in positive attitudes to seeking mental health care using the Attitudes Toward Mental Health Treatment (ATMHT) scale as a secondary outcome of increased empowerment.
 - b. increase in intentions to seek out social support as a secondary outcome of increased empowerment.
- 5) Social Connection
 - a. Increase in the general sense of belonging using the General Belongingness Scale (GBS)
 - b. Increase in perceived social support using the Multidimensional Scale of Perceived Social Support (MSPSS)

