
Potential participants interested in participating in the study will first complete an eligibility screener. Those participants that are deemed eligible based on inclusion/exclusion criteria will be contacted by a study team member to schedule a virtual baseline visit.

Participants will complete 2 online surveys during the study: at baseline and after completion of the critical narrative development (about 1 month after initial enlistment into the study). Assessments will take 20-25 minutes to complete. The primary goal of the two surveys will be to assess the preliminary effectiveness of the critical narratives at impacting depression, anxiety, self-esteem, psychological well-being, and empowerment. All surveys will be housed and implemented through REDCap. Below is a table of the measures utilized in the surveys.

Construct	Measure	Description	Citation	Time Point	
				Baseline	1-Month
Depression Symptoms	Patient Health Questionnaire (PHQ-9)	The PHQ-9 is a 9-item depression symptom checklist scored from 0 to 3 on a Likert scale of "not at all" to "nearly every day." The PHQ-9 has demonstrated high internal reliability ($\alpha = .88$) and test-retest reliability ($\alpha = .94$)	Kroenke, K., Spitzer, R.L., & Williams, J.B. (2001). The PHQ-9: Validity of a brief depression severity measure. Journal of General Internal Medicine , 16(9), 606-613.	X	X
Anxiety Symptoms	Generalized Anxiety Disorder (GAD-7)	The GAD-7 is a 7-item measure designed to assess anxiety symptoms scored from 0 to 3 on a Likert scale of "not at all" to "nearly every day," with total scores ranging from 0 to 21. The	Spitzer, R.L., Kroenke, K., Williams, J.B., & Lowe, B. (2006). A brief measure for assessing generalized anxiety disorder: the GAD-7.	X	X

		GAD-7 is valid with intercorrelations with the PHQ-2 ($r = .64$) and the Rosenberg Self-Esteem Scale ($r = .43$) and has good reliability ($\alpha = 0.89$; Lowe et al., 2008).	Archives of internal medicine, 166 (10), 1092-1097.		

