Participants provide consent for the research team to retain email addresses and phone numbers for participant follow-up. During the baseline visit, participants will be scheduled for a 1-month follow-up visit, including an interview, survey, and final submission of the critical narrative. A week before the scheduled 1-month follow-up, a research team member will reach out to the participant to confirm the 1-month study visit via phone, e-mail, or text as indicated in the participant's preferred contact method. A research team member will reach out every two days for confirmation until received from the participant. This will aid in ensuring confirmation of the scheduled follow-up and retention of participants at the follow-up time point.

STUDY PROCEDURES:

Detailed Description:

The research activities involve a two-arm pilot enrolling a sample of 30 participants who identify as SGM, POC, and living with moderate to severe depression. After consent and completion of the baseline survey (15-20 min) and interview (45-60 min), participants will be randomized into one of two critical narrative interventions: photo-novella (n=15) or digital storytelling (n=15).

All participants will be given the same two prompts for their narrative intervention asking, "Share an experience of when you have felt seen as an SGM Person of Color." AND "share an experience of when you have felt unseen as an SGM person of color."

Photo-Novella: Participants in the photo-novella intervention will be asked to tell their story through 12 photographs and a caption (6 for the first prompt and 6 for the second prompt). Participants will be instructed to take a photograph answering the two prompts. Participants may use their smartphones or digital camera to capture their photographs. Participants may also edit their photographs using photo-editing software for aesthetics. Participants will also be asked to provide a short caption (no more than two sentences) explaining their photograph and provide a title for their work. Participants will be provided with a basic guide on photography and how to "snap a picture."

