Participants will receive a link via email a day before their one-month follow-up visit to complete a follow-up survey (15-20 mins). During the one-month follow-up, a research team member virtually on Zoom will conduct a follow-up interview (45-60 mins) asking participants about their experience of creating their critical narrative piece. At the one-month follow-up, research team members will review the final critical narratives of the participants digitally. Two days before the one-month follow-up, participants will receive a link via email to a Box folder (that is HIPAA compliant) where they can upload their photos/videos.

The participants will be notified of the gallery date and invited to attend. The gallery is optional and does not impact participation in the study.

Use of Deception:

Not applicable. This study does not utilize deception.

Statistical Analysis:

Prior to conducting our multivariate analyses, we will examine study variables using descriptive statistics and test for differences across demographic characteristics (e.g., race/ethnicity, age, education) using t-tests, ANOVAs, and Chi-squares, as appropriate. As participants will be randomized to the two groups, systematic baseline differences are not expected; however, if some parameters differ across conditions at baseline, they will be included as covariates in subsequent multivariate models.

As appropriate, we will compare differences from baseline to the 1-month outcomes across our outcome measures using t-tests and Chi-squares. We will also estimate the effect size of our interventions to aid us in determining the future sample size needed for a larger study on the intervention.

Power analysis

Due to the exploratory nature of this study, a power analysis was not conducted for an a priori sample size. However, we will be conducting in-depth interviews until we reach saturation. Typical saturation for in-depth interviews is determined as between 9-17 participants (Hennink & Kaiser, 2022), therefore, we will recruit a total of 30 participants (15 participants for each condition).

RISK/BENEFIT ASSESSMENT:

1. Risks:

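### The t-tests on baseline-to-1-month differences have no stated contrast (between arms, within arm or pooled), baseline adjustment is not prespecified, and the effect size meant to size a larger study is tied to no comparison

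*Combined protocol and SAP*

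**What the plan says.** The outcome analysis is one sentence in Study Procedures, Statistical Analysis: "we will compare differences from baseline to the 1-month outcomes across our outcome measures using t-tests and Chi-squares". On covariates, the same section says that "if some parameters differ across conditions at baseline, they will be included as covariates in subsequent multivariate models". It does not define those models. The baseline tests it describes concern demographic characteristics, so it is unclear whether the parameters include baseline outcome scores. The section adds: "We will also estimate the effect size of our interventions to aid us in determining the future sample size".

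The aims do not settle the contrast:
- **Outcomes section:** "Aim 2 will evaluate the impact of CN assignment (photo-novella or digital storytelling". This leans towards a comparison between arms.
- **Study Design, Aim 2:** it asks for the change seen after each of the assigned formats. This leans towards change within each arm.
- **Objectives, specific aim 2:** "Evaluate the impact of CN on empowerment (e.g., self-esteem) and mental health outcomes". Study Instruments is similar: "The primary goal of the two surveys will be to assess the preliminary effectiveness of the critical narratives". Both ask about narratives as such, which fits change pooled over arms or within each arm.

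The Detailed Description says "All participants will be given the same two prompts for their narrative intervention". The arms differ in format, and neither is an untreated control.

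**The concern.** The three readings answer different questions. A between-arm test compares photo-novella with digital story and uses the randomisation. Within-arm and pooled tests ask whether scores move after making a narrative. That is closer to the primary objective, but it has no control. The plan then carries forward an effect size without saying which question it answers, and it does not say what the larger study will compare. A pre-post change used as if it were a difference between arms would mis-size that study.

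Two further points follow. If the test is between arms, the plan gives up precision that the baseline scores it already collects could supply, because covariate adjustment depends on whether the arms happen to differ. If the test is within arm, PHQ-9 change is exposed to regression to the mean, because entry requires a score of 10 or higher.

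**Working it through.** **Inputs from the documents.** 30 participants are randomised 1:1, 15 per arm. Expected retention is 80% or greater (Early Withdrawal of Subjects), so 0.80 × 15 = 12 per arm at the lower end. PHQ-9 entry is 10 or higher (Key Inclusion Criteria). The plan gives no SD, correlation, alpha or power. It states that no power analysis was done, so there is no power-based figure to reproduce.

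**Assumptions.** The baseline-to-1-month correlation r runs from 0.3 to 0.8. SDs are equal at both visits. Tests are two-sided at 5%. Effects are in SD units.

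**1. The contrast matters.** At 15 per arm and r = 0.5, the SD of change is √(2(1−r)) = 1. The effect detectable with 80% power is then 0.53 SD for pooled change (30 people), 0.78 SD for change in one arm (15 people) and 1.06 SD for the difference in change between arms.

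**2. Between-arm change score against ANCOVA, 12 per arm.**
- Change-score variance factor: 2(1−r).
- ANCOVA variance factor: (1−r²) × [1 + 1/(2n−4)]. At n = 12 the bracket is 1 + 1/20 = 1.05, the small-sample cost of estimating the slope.
- 95% CI half-width: t × √(2/12 × factor), with 22 df for change and 21 df for ANCOVA.

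| r | Change | ANCOVA | Variance ratio | Half-width, change | Half-width, ANCOVA |
|---|---|---|---|---|---|
| 0.3 | 1.40 | 0.956 | 1.47 | 1.00 SD | 0.83 SD |
| 0.5 | 1.00 | 0.788 | 1.27 | 0.85 SD | 0.75 SD |
| 0.7 | 0.60 | 0.536 | 1.12 | 0.66 SD | 0.62 SD |
| 0.8 | 0.40 | 0.378 | 1.06 | 0.54 SD | 0.52 SD |

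Simulation (40,000 replicates) gave 1.46, 1.26 and 1.11 for the first three ratios.

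**3. The same comparison for PHQ-9.** The entry cut narrows the baseline spread. Scores were simulated as rounded normal on 0–27, with an assumed screened-population mean of 8–12 and SD of 5–6. Variance ratios at r = 0.3, 0.5, 0.7 and 0.8 were:
- Separate screener, correlated 0.8 with baseline: 1.26–1.30, 1.14–1.17, 1.05–1.07, 1.00–1.03.
- Baseline score itself cut at 10: 1.10–1.20, 1.04–1.10, 1.00–1.03, 0.99–1.01.

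**4. Regression to the mean in PHQ-9 change, no intervention effect.** If the qualifying score is the baseline score, the expected fall is (1−r) × SD × λ(c). Here c = (9.5 − mean)/SD and λ is the normal density divided by the upper tail probability.
- Mean 8, SD 6, r = 0.5: c = 0.25, λ = 0.96, fall = 0.5 × 6 × 0.96 = 2.9 points.
- Mean 12, SD 5, r = 0.8: c = −0.5, λ = 0.51, fall = 0.2 × 5 × 0.51 = 0.5 points.

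Study Instruments describes a screener first, after which eligible people "will be contacted by a study team member to schedule a virtual baseline visit". Part of the fall could then occur before baseline. With screener and baseline correlated 0.8 and correlation decaying over time, these falls are multiplied by 0.8, to about 2.3 and 0.4 (simulated on the 0–27 scale: 2.2 and 0.4). If the screener correlates equally with baseline and 1-month scores, the fall is zero.

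**5. If formats were compared by separate within-arm tests.** Suppose both formats produce the same true change of 0.5 SD, with 12 per arm. The noncentrality is 0.5 × √12 / √(2(1−r)) = 1.46, 1.73 and 2.24 at r = 0.3, 0.5 and 0.7. Power per arm is p = 0.267, 0.353 and 0.532. The chance that exactly one arm is significant is 2p(1−p) = 39%, 46% and 50%.

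**The case against.** The strongest reply is that this is an exploratory pilot with no power analysis. A change-score test is valid, and a half-width of 0.75 rather than 0.85 SD is imprecise either way. That stands: ANCOVA is a modest refinement, nearly worthless for PHQ-9 at r = 0.8, and it does not turn 30 people into a powered comparison. It also cannot answer whether narratives help, since both arms make one. Only pooled or within-arm change bears on that, so the pooled estimate must be part of the fix.

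A reader might infer more than the documents support:
- **That baseline scores are ignored unless the arms differ.** A change score uses baseline by subtraction, and the covariate rule is attached to the undefined multivariate models, not to the t-tests. Counting how often a chance imbalance goes unadjusted applies only if 1-month scores are compared without using baseline, which is neither a change-score nor a paired test.
- **That PHQ-9 change will certainly be inflated.** The size rests on an assumed population and correlation pattern, and it can be zero.
- **That the sponsor intends to compare formats through separate within-arm tests, or to use a pre-post change as a between-arm effect.** Nothing says so. The plan merely leaves both open.

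What the reply does not remove is the ambiguity. In a pilot without a power analysis the estimates are the main quantitative product, so the contrast should be named.

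**Conclusion.** The concern holds in this form. No part of the documents fixes the contrast for the t-tests or prespecifies adjustment for the baseline score, and the effect size intended for a larger study is unlabelled. That conclusion rests on the text alone.

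The sizes in the working depend on the assumed correlations, equal SDs (except the PHQ-9 simulations) and 12 completers per arm. The between-arm precision loss ranges from moderate to negligible. Regression to the mean in uncontrolled PHQ-9 change depends as well on the assumed population and on how the three scores correlate. The 39–50% chance of a misleading split applies only if separate within-arm tests were used to compare formats.

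The plan should be changed, but the trial is not invalid as it stands, and a between-arm change-score test would not be wrong.

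**What to change.** 1. For each of the ten named Aim 2 scales measured at both visits, prespecify that the photo-novella versus digital story difference will be estimated by regressing the 1-month score on randomised arm and the baseline score of the same scale, with a 95% CI. Delete the rule that adds covariates when arms differ at baseline. Intention to seek social support has no named scale, so this cannot be applied to it until one is given.
2. Report pre-post change pooled over both arms and within each arm, by paired methods with 95% CIs. Present it as the quantity bearing on the primary objective, labelled uncontrolled and, for PHQ-9, open to regression to the mean.
3. State that no difference between formats will be inferred from separate within-arm tests.
4. Report the SD and the baseline-to-1-month correlation for each scale. State which contrast each effect size describes, so that the one carried forward matches the larger study's comparison.

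The cost is a few sentences and one degree of freedom per model, with no new data or visits.

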There is a need to develop interventions for SGM EA of color that empower them to seek out support and treatment for their mental health concerns. Narratives or storytelling is a fundamental experience formed by individuals to understand and make sense of the world around them. The creation of personal narratives has been associated with several health benefits, including an increased sense of self-efficacy, increased social support, and improved mental and physical health. Critical Narrative Intervention (CNI) is a distinct approach for marginalized communities to create a group narrative that has been found to increase empowerment and social support for participants. Recent CNI research methods have focused on sexuality and sexual health, mothering and substance use, and reproductive justice.

However, the use of CNs as an elicitation strategy has not been examined for increasing mental health treatment seeking within SGM EA of color; therefore, this pilot study will examine CNs from SGM EA of color and it's the potential to increase empowerment (including self-efficacy) and reduce mental health symptoms (depression and anxiety) as an elicitation strategy for increasing intentions to seek support (personal and professional). The proposed pilot study will also examine the feasibility, acceptability, and appropriateness of critical narratives as a strategy for SGM racial/ethnic minorities and address mental health disparities.

CHARACTERISTICS OF THE STUDY POPULATION:

1. Target Population and Accrual:

The target population for this study includes sexual and gender minority emerging adults of color who identify as living with depression in the United States. For the proposed study, we expect to screen about 200 individuals over the 6 months and consent and randomize 30 participants in a 1:1 assignment.

2. Key Inclusion Criteria:

1) identify as a sexual minority; (2) live in the United States; (3) identify as a person of color; (4) be aged 18-24 years; (5) have a smartphone and or computer access; (6) identify as living with moderate to severe depression as indicated on the PHQ-9 (score of 10 or higher); and (7) do not report suicidal ideation in the past month.

3. Key Exclusion Criteria:

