Ads will link interested individuals to the study's eligibility screener to verify their eligibility. We have recruited through these platforms for over a decade with a significant track record of demonstrated success. We plan to use lessons learned from these efforts to guide the implementation of our proposed recruitment strategy.

If necessary, we will leverage our connections in the national LGBTQ+ community and conduct in-person or e-mail recruitment and word-of-mouth referrals. We will also hang flyers in local areas including on campus, businesses, and public spaces (as allowed).

The eligibility screener will be a REDCap survey that asks participants to fill out demographic information related to inclusion and exclusion criteria. The eligibility screener will also ask participants to provide contact information (Name, phone number, email address, preferred contact method, and time of day available for contact) for a study member to reach out to them if they are eligible and to schedule a baseline visit. The screener will also ask for participants to provide their longitude and latitude to be eligible for the study. This information will be used to confirm that they are eligible and live within the United States.

5. Early Withdrawal of Subjects:

Retention during a longitudinal study is expected to be 80% or greater. Participation in the study is voluntary; therefore, a participant may withdraw from the study at any time by communicating with the study team via phone or email. The research team member will work to communicate and keep in touch with participants throughout the study. However, if the research team member is unable to reach a participant after extensive attempts or the participant fails to attend follow-up visits, the participant may be withdrawn from the study.

6. Vulnerable Populations:

This research study does not include children, pregnant women, fetuses, neonates, or prisoners.

7. Populations vulnerable to undue influence or coercion:

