Using online recruitment methods where the intervention is not pitched by a recruiter minimizes the risk of potential coercion. Instead, SGM EA of color can choose and click on the recruitment advertisement and decide if they wish to learn more. Similarly, staff will be trained to discuss all elements of the consent process with potential participants. Consent documents will fully explain the study procedures, potential risks, and potential benefits. Participants will also be reminded that the study participation is voluntary and that refusing to participate in the study or withdrawing from the study is an option at any time.

STUDY DESIGN:

Critical narratives have not been examined for addressing psychological outcomes (e.g., depression, anxiety, self-esteem, empowerment, psychological well-being) within SGM EA of color; therefore, this pilot study will examine the use of CNIs to impact SGM of color psychological outcomes. Prior literature has shown that CNIs have the potential to increase

empowerment, self-efficacy, and social support as a prevention strategy for mental health. The study design will utilize mixed methods to address two aims:

- Aim 1) Examine the experiences of discrimination and acceptance of SGM EA of color living with depression and its impact on seeking mental health treatment,
- Aim 2) Evaluate the change in psychological and well-being outcomes (depression, anxiety, self-esteem, empowerment, and psychological well-being) of SGM individuals of color after each CNI assignment.
- Aim 3) Understand the acceptability, appropriateness, and feasibility of critical narrative development as an intervention for SGM EA of color.

Below is a timeline of the study, including study assessments and how they address one of the three aims:

Critical Narrative Intervention Timeline and Study Design			
Month(s)	Timepoint	Measure/Study Procedure	Aim(s) Addressed
1-6	Recruitment	Eligibility Screener	N/A
2-8	Baseline	Baseline Survey (n=30) Individual Interview (n=30) Randomization Photo-novella, n=15 Digital storytelling, n=15	Aim 2 Aim 1
3-10	1-month	1-Month Follow-up Survey (n=30) Individual Interview (n=30)	Aim 2 and Aim 3 Aim 3

The entire study will last about 10 months from recruitment to final collection of all critical narratives. A participant's time in the study will last about one month from enrollment during baseline to completion of the post-intervention visit and presentation of their critical narrative.

METHODS:

1. Study Instruments:

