The potential risks to participants are detailed as follows: Some participants may be uncomfortable answering questions about their past and/or current mental health, psychiatric symptoms, or risk behaviors (e.g., sexual behavior, substance use). Participants may also feel uncomfortable answering questions about their sexual attractions or their sexual and gender identity. However, it is important to note that an emotional discomfort is an event encountered routinely in daily life, and potential discomfort would likely not exceed what is typically encountered in these youths' experiences. All information

used in enrollment and recruitment describing the research activities will include a detailed description of the content and expected participation of the respondent, such that the respondent is aware of the nature of the questions to be included in the surveys.

2. Benefits:

SGM EA of color in the study may benefit through the process of developing their critical narratives with the potential to reflect on their experiences and behaviors. Furthermore, participation in the proposed study could potentially benefit participants in a few important ways. It is possible that the interview about their experiences and/or the CNI activity may be cathartic in nature as it may be the first time or opportunity allowing SGM EA of color to speak about their experiences. Others will benefit because the study will result in increased knowledge about narrative interventions to address mental health disparities among SGM EA of color and can inform interventions to address mental health concerns at large. In sum, the potential benefits of the research far outweigh the risks for the participants.

3. Subject Privacy:

Informed consent documents will inform research participants of the need to keep answers to questions confidential. Participants will have the option to refuse to answer or skip any questions on the surveys that they are uncomfortable answering. They will also be informed about the limits of confidentiality as it relates to imminent suicide risk or risk of imminent harm to others and the need to enact emergency procedures to ensure their safety and the safety of others. Psychological distress is a potential risk to SGM EA during the completion of the interviews or surveys, during the creation of their narratives, and during post-intervention visits (about one month after baseline).

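### The t-tests on baseline-to-1-month change use only participants with both surveys, so the within-arm change and the effect size for planning are completers-only; the bias is conditional and modest, and the remedy is cheap

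*Combined protocol and SAP*

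**What the plan says.** Sample: the protocol will "consent and randomize 30 participants in a 1:1 assignment", 15 per arm.

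Target: in Study Design, Aim 2 is to "Evaluate the change in psychological and well-being outcomes" after each assignment. That is a change within each arm.

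Analysis: under Statistical Analysis, "we will compare differences from baseline to the 1-month outcomes across our outcome measures using t-tests and Chi-squares". The same section adds: "We will also estimate the effect size of our interventions to aid us in determining the future sample size needed for a larger study". It also mentions multivariate models. Their only stated feature is that variables which differ at baseline enter as covariates.

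Loss: Early Withdrawal of Subjects states "Retention during a longitudinal study is expected to be 80% or greater", and that if "the participant fails to attend follow-up visits, the participant may be withdrawn from the study". The Study Design timeline nevertheless shows "1-Month Follow-up Survey (n=30" at one month, which is no loss at all. Under Subject Privacy, "Participants will have the option to refuse to answer or skip any questions on the surveys".

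Survey delivery: Study Procedures has the 1-month survey emailed as a link the day before the visit, so completing it does not require attending.

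The documents contain no analysis set, intention-to-treat statement, imputation, likelihood model that keeps incomplete cases, comparison of those with and without follow-up, or missing-data sensitivity analysis.

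**The concern.** A change score needs two measurements. Anyone without a 1-month survey leaves the test, and their observed baseline goes with them. If those who leave differ in severity or in response, the mean change among those who stay is not the mean change of those randomised. Because Aim 2 is worded within each arm, equal loss in both arms does not cancel this.

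The withdrawal provision can add avoidable loss. A person who misses the video visit could still answer the emailed survey, but the protocol does not say that the survey would still be sought or used after withdrawal.

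At stake are the change reported as the impact of the narratives and the effect size taken forward to size the next trial.

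**Working it through.** **The plan's own figures.** 2 x 15 = 30 agrees wherever the sample size is stated. There is no power calculation to reproduce; 30 comes from interview saturation. At the stated retention floor, 30 x 0.80 = 24 people (15 x 0.80 = 12 per arm) have a change score, and up to 6 do not.

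**Inputs not in the documents (assumptions).** PHQ-9 SD 4.5 at both times; baseline to 1-month correlation 0.5; true mean change -2.0; scores bivariate normal; logistic dropout with odds ratio (OR) 1.5 to 3 per SD of the score that drives it; 10 to 20% loss.

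**Quantity checked.** Bias = mean change among those with both scores minus mean change among all randomised. It was simulated in SD units with 2,000,000 draws, then converted as completers' change = -2.0 + 4.5 x bias. Example, dropout driven by baseline, OR 2: -2.0 + 4.5 x 0.064 = -1.71.

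Results at 20% loss (truth -2.0). The likelihood estimate uses all baselines.

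| Dropout depends on | Estimate | OR 1.5 | OR 2 | OR 3 |
|---|---|---|---|---|
| Baseline severity | completers | -1.82 | -1.71 | -1.58 |
| | likelihood | -2.00 | -2.00 | -2.00 |
| 1-month score | completers | -2.18 | -2.29 | -2.42 |
| | likelihood | -2.27 | -2.44 | -2.65 |
| Lack of improvement | completers | -2.35 | -2.58 | -2.83 |
| | likelihood | -2.27 | -2.44 | -2.65 |

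At OR 1 every entry is -2.0. At 10% loss and OR 2, completers give -1.85 (baseline) and -2.30 (lack of improvement). At 10% loss and OR 1.5 the three mechanisms give about -1.9, -2.1 and -2.2.

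**Other correlations.** Over correlations of 0.3 to 0.7 at 20% loss, the completers' bias is +0.02 to +0.13 SD (baseline), -0.02 to -0.13 SD (1-month score) and -0.06 to -0.22 SD (change). The largest is 0.22 x 4.5 = 0.99 points.

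**Against sampling error.** SD of change = 4.5 x sqrt(2 x (1 - 0.5)) = 4.5. Standard error with 24 completers = 4.5 / sqrt(24) = 0.92; within one arm of 12 it is 4.5 / sqrt(12) = 1.30. The largest bias in the table is 0.83. For the 0.99-point case (correlation 0.3), the SD of change is 4.5 x sqrt(1.4) = 5.32, and the standard error with 24 is 1.09.

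**Between arms** (correlation 0.5, dropout driven by the 1-month score). With 20% loss in each arm the bias is about 0. With 30% against 10% loss and OR 2 to 3 it is about -0.06 to -0.09 SD, or 0.3 to 0.4 points.

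**Setting dropouts to no change.** This multiplies the completers' change by 0.8. Baseline-driven, OR 3: 0.8 x -1.58 = -1.26, further from the truth than completers. Driven by lack of improvement, OR 3: 0.8 x -2.83 = -2.26, closer. Unrelated to symptoms: 0.8 x -2.0 = -1.60, a bias where completers had none.

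**Effect on planning.** Required n scales with 1 / d². With the SD held at 4.5, a later study sized on the within-person change at OR 3 and 20% loss would have (2.0 / 1.58)² = 1.60 times the needed n under baseline-driven dropout, and (2.0 / 2.83)² = 0.50 times under dropout driven by lack of improvement.

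**The case against.** The strongest reply is that this is an exploratory pilot sized for interviews, and that the bias is smaller than its sampling error. That stands, and it limits the weight of the point. It does not remove it: the estimate is carried into the next design, and the change costs little.

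Second, a reader might infer that the plan declares a completers-only analysis. It does not. That is the consequence of the named test when nothing else is specified. The multivariate models might have kept incomplete cases, but no such role is stated.

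Third, a reader might blame the withdrawal rule. It is permissive, and nothing says that collected data are discarded. The missing survey is the cause, and the rule only contributes. Repeated contact until the visit is confirmed (Subject Follow-up) and the higher payment at one month (Compensation) already work to limit loss. They reduce the number missing but do not say how those still missing are analysed.

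Fourth, a mixed model is not a cure. It removes the bias when dropout depends on baseline, removes only part of it when dropout depends on lack of improvement, and is worse than completers when dropout depends on the 1-month score. This objection stands in full. It is why the completers' result should be kept alongside and why a sensitivity range is needed.

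Fifth, since questions may be skipped, a reader might infer heavy loss of scale scores. The documents give no skipping rate and do not say that a scale with one blank item is dropped, so no figure for that loss can be supported.

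**Conclusion.** The point holds as a cheap improvement. The named t-tests, with up to 20% loss expected and nothing to bring the missing back, make the within-arm change and any effect size built on it completers-only. Under the stated assumptions the PHQ-9 change is understated by about 0.1 to 0.4 points if the more severe at baseline leave. It is overstated by about 0.1 to 0.4 points if those worse at one month leave, and by 0.2 to 0.8 points if those who do not improve leave. The direction cannot be known in advance.

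Twenty percent is the worst loss that the protocol expects, and OR 3 is the strong end of the selection assumed. The normal baseline also ignores the PHQ-9 entry score of 10, so the figures are indicative.

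A reader might go further and infer that the randomised comparison of the two narrative forms is biased. The calculation does not support that when loss and its mechanism are alike in both arms, and the documents give no reason to expect a difference.

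**What to change.** 1. In Early Withdrawal of Subjects, state that missing the visit does not end outcome collection. The emailed 1-month survey is still sent and reminded, and any returned survey is analysed as randomised unless the participant withdraws consent. Reconcile the timeline's 30 at one month with the 80% retention figure.

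2. In Statistical Analysis, make the main analysis one linear mixed model per scale, with baseline and 1-month scores as outcomes, terms for time and time-by-arm, and all 30 randomised included. Report the completers' t-test alongside. Compare the baseline scores of those with and without 1-month data.

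3. Add a sensitivity analysis over a range of assumed 1-month values for those missing, with no change as one point and not the sole check. Carry that range into the effect size used for planning.

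4. For skipped items, follow each scale's own scoring rule and say so.

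The cost is a few sentences and slightly more analysis work, with no added participants or visits. The main model relies on a missing-at-random assumption, and the effect size may come out less favourable. The text should be settled before outcome data are seen.
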